1.4 BENEFIT / RISK ASSESSMENT

Patients assigned to the PhI group will receive tenecteplase combined with antiplatelet

(acetylsalicylic acid), antithrombin (enoxaparin) treatment and clopidogrel 300 mg. Thereafter they will undergo cardiac catheterisation within 6-24 hours or rescue coronary intervention as required and, if indicated, stent implantation.

As previously indicated, fibrinolysis is a well-established treatment recommended by clinical guidelines. The main risk associated with fibrinolytic treatment is bleeding. Patients will be carefully screened to minimise bleeding risk. Hence in the current study, patients ≥ 60 years, who are known to have an increased bleeding risk⁴⁴, will receive half-dose tenecteplase. As was the case in STREAM-1, the initial bolus of enoxaparin will be omitted to conform to the evidence-based strategy of the ExTRACT trial^{25, 27, 29} which supports this approach as safe and effective. Based on the study of Larson et al²⁰ attesting to the safety of $\frac{1}{2}$ dose fibrinolytic and a 600 mg loading dose of clopidogrel in elderly patients, clopidogrel 300 mg will be administered in Group PhI. In addition, patients with low body weight (i.e. below 55 kg) will be excluded to minimise the small but definitive risk of ICH noted from prior trials. Insufficient reperfusion or vessel reocclusion after fibrinolysis will be addressed, as per current guidelines, by measuring ST-segment resolution. Patients who do not show ECG and/or clinical evidence of adequate reperfusion 90 min after bolus tenecteplase will undergo prompt rescue PCI.

Patients randomised to PPCI will be treated in accordance with international PCI guidelines in the prehospital setting. PPCI is a routine treatment in patients with STEMI and will therefore serve as a comparator to the PhI arm. It has been shown to be safe and effective in securing and maintaining coronary artery patency. Patients with contraindications will be excluded.

During the course of the trial a Data Safety Monitoring Board (DSMB) will review, on a regular basis and whenever necessary, all safety data and evaluate the patients' safety and possible risks. The DSMB will report to the Executive Committee and is entitled to recommend any measures required to secure the patients' safety.

2. TRIAL OBJECTIVES

2.1 GENERAL AIM

This study will evaluate the efficacy of 2 reperfusion strategies based on ST-segment resolution in patients ≥ 60 years presenting with acute STEMI within 3 hours of symptom onset in a pre-hospital setting/community hospital. Following randomisation to a strategy of early (pre-hospital) tenecteplase and additional enoxaparin and a loading dose of clopidogrel, patients will undergo cardiac catheterisation within 6-24 hours with timely coronary intervention as appropriate (or by rescue coronary intervention if required) in Group PhI. Patients randomized to group PPCI will receive concomitant antithrombotic treatment according to local practice. The efficacy will be evaluated by ST-segment resolution (cfr infra), TIMI flow grades and need for rescue PCI (in PhI group).

Clinical events i.e. death, shock, heart failure, recurrent MI and aborted MI will be recorded and assessed as single or composite endpoints for evaluation as noted in the statistical analytical plan. All statistical tests on clinical events are of exploratory nature based on descriptive p-values with estimation of 95% confidence limits for formal statistical hypotheses generation. For comparison the same composite clinical event rates (for example the composite of death, shock, congestive heart failure and re-infarction = primary endpoint of STREAM-1) will be analysed (see APPENDICES).

2.2 EFFICACY ENDPOINT

The trial is of exploratory nature with the aim to examine the potential benefits of this pharmacoinvasive strategy. Therefore, no confirmatory statistical hypothesis is pre-specified. All statistical tests are of exploratory nature based on descriptive p-values with accompanying 95% confidence limits for formal statistical hypotheses generation. Efficacy for early reperfusion will be evaluated by the number of patients achieving $\geq 50\%$ ST-segment resolution before and after PCI in lead with maximal ST elevation at baseline; % rescue PCI; TIMI flow grades.

An intent-to-treat analysis of all randomised patients will be carried out. After 50 % of the planned recruitment a formal interim analysis will be performed by the DSMB to evaluate and advise the Executive Committee on the feasibility and justification of enlarging the sample size with provision to proceed with a confirmatory trial.

3. DESCRIPTION OF DESIGN AND TRIAL POPULATION

3.1 OVERALL TRIAL DESIGN AND PLAN - DESCRIPTION

The current trial is designed as an open-label, prospective, randomised, parallel, comparative international multi-centre trial.

In patients ≥ 60 years with acute ST-elevation myocardial infarction randomised within 3 hours of onset of symptoms, the efficacy and safety of a strategy of early fibrinolytic treatment with half-dose tenecteplase and additional antiplatelet and antithrombin therapy followed by catheterisation within 6-24 hours or rescue coronary intervention as required will be compared to a strategy of PPCI according to local standards.

STUDY PROTOCOL STREAM 2

STEMI ≥ 60 y, <3 h from symptom onset, ≥ 2 mm ST segment elevation in ≥ 2 leads,
UNABLE TO UNDERGO PPCI WITHIN 1 H

[figure not shown]

Figure 4: Overall Trial Design

3.2 DISCUSSION OF TRIAL DESIGN, INCLUDING THE CHOICE OF CONTROL GROUPS

Although several studies and registries have compared fibrinolytic treatment with PPCI in patients with acute myocardial infarction, limited trial data are available in older patients ≥ 60 years regarding the strategy of early fibrinolysis followed by PCI versus a strategy of PPCI, in particular in the pre-hospital setting.^{5, 10, 18, 42} Moreover, limited data exists concerning the efficacy and safety of a loading dose of clopidogrel combined with fibrinolytic therapy in such patients.

The groups of interest are:

- Group Phi: fibrinolytic treatment with half-dose tenecteplase combined with clopidogrel 300 mg and followed by catheterisation within 6-24 hours or rescue coronary intervention as required.
- Group PPCI: PPCI according to local standards.

3.3 SELECTION OF TRIAL POPULATION

Patients with ST-elevation acute myocardial infarction (STEMI) within 3 hours of symptom onset in the pre-hospital setting will be randomised to Group PhI for a strategy of early pre-hospital/ER community hospital fibrinolysis or to PPCI, if the eligibility criteria mentioned below are met.

Approximately 600 patients (400 patients to group PhI and 200 patients to group PPCI) will be enrolled in approximately 65 sites located in different countries (for sample size calculation see section 7). A minimum of 100 patients \geq 70 years of age will be randomized to the PhI arm

3.3.1 Inclusion criteria

1. Age equal or greater than 60 years
2. Onset of symptoms $<$ 3 hours prior to randomisation
3. 12-lead ECG indicative of an acute STEMI (ST-elevation will be measured from the J point; scale: 1 mm per 0.1 mV):
 - \geq 2 mm ST-elevation across 2 contiguous precordial leads (V1-V6) or leads I and aVL for a minimum combined total of \geq 4 mm ST-elevation
or
 - \geq 2 mm ST-elevation in 2 contiguous inferior leads (II, III, aVF) for a minimum combined total of \geq 4 mm ST-elevation
4. Informed consent received

3.3.2 Exclusion criteria

1. Expected performance of PCI $<$ 60 minutes from diagnosis (qualifying ECG) or inability to arrive at the catheterisation laboratory within 3 hours
2. Previous CABG
3. Left bundle branch block or ventricular pacing
4. Patients with cardiogenic shock - Killip Class 4
5. Patients with a body weight $<$ 55 kg (known or estimated)
6. Uncontrolled hypertension, defined as sustained blood pressure \geq 180/110 mm Hg (systolic BP \geq 180 mm Hg and/or diastolic BP \geq 110 mm Hg) prior to randomisation
7. Known prior stroke or TIA
8. Recent administration of any i.v. or s.c. anticoagulation within 12 hours, including unfractionated heparin, enoxaparin, and/or bivalirudin or current use of oral anticoagulation (i.e. warfarin or a NOACs)
9. Active bleeding or known bleeding disorder/diathesis
10. Known history of central nervous system damage (i.e. neoplasm, aneurysm, intracranial or spinal surgery) or recent trauma to the head or cranium (i.e. $<$ 3 months)

11. Major surgery, biopsy of a parenchymal organ, or significant trauma within the past 2 months (this includes any trauma associated with the current myocardial infarction)
12. Clinical diagnosis associated with increased risk of bleeding including known active peptic ulceration and/or neoplasm with increased bleeding risk
13. Known severe renal insufficiency
14. Prolonged cardiopulmonary resuscitation (> 2 minutes) within the past 2 weeks
15. Known acute pericarditis and/or subacute bacterial endocarditis
16. Known acute pancreatitis or known severe hepatic dysfunction, including hepatic failure, cirrhosis, portal hypertension (oesophageal varices) and active hepatitis
17. Dementia
18. Previous enrolment in this study or treatment with an investigational drug or device under another study protocol in the past 7 days
19. Known allergic reactions to tenecteplase, clopidogrel, enoxaparin and aspirin
20. Inability to follow the protocol and comply with follow-up requirements or any other reason that the investigator feels would place the patient at increased risk if the investigational therapy is initiated.

4. TREATMENTS

4.1 TREATMENTS TO BE ADMINISTERED

4.1.1 Identity of investigational products

Tenecteplase (Metalysé®) manufactured by Boehringer Ingelheim (Metalysé®) or Genentech Inc. (TNKase®), will be taken off the shelf or made available according to local regulations. Vials contain either 50 mg or 40 mg of tenecteplase lyophilized powder and excipients, L-arginine, phosphoric acid and polysorbate 20, for reconstitution with sterile water from a 10 mL or 8 mL vial, respectively

Clopidogrel will be taken off the shelf. Tablets contain 75 mg of clopidogrel for oral use. 1 tablet containing 300 mg clopidogrel can be given as loading dose instead of 4 tablets of 75 mg.

4.1.2 Methods of assigning patients to treatment groups

Immediately after screening in the pre-hospital setting, eligible patients will be randomised 2:1 to the pharmaco-invasive therapy or to PPCI.

Randomisation will be performed centrally by means of an interactive voice response system (IVRS), which has to be called by the investigator or an authorised member of site staff.

4.1.3 Selection of doses in the trial

Tenecteplase is given in a weight-adjusted dose regimen as described in the following section (4.1.4) according to the Basic Product Information.⁴⁵ Based on the strategy used by Larson et al.²⁰ and after balancing the risks versus benefits the dose has been adapted for patients \geq 60 years of age who will receive half dose tenecteplase. As described below, the strategy of measuring ST-segment resolution at 90-minutes after fibrinolysis, or earlier if clinically indicated and performing rescue PCI, if appropriate, in Group Phi is considered to provide an optimal balance between efficacy and safety.

Based on the results of the ASSENT-3 and ExTRACT trials (please refer to section 1.2 for details) reduced dose of LMWH enoxaparin will be used in the current trial.).^{25, 26} In the ExTRACT trial, the dose of enoxaparin was reduced for patients of at least 75 years of age, which resulted in positive overall results for this age group. To conform to these results the initial intravenous bolus of enoxaparin will be omitted and a reduced daily dose of enoxaparin (0.75 mg/kg instead of 1 mg/kg) will be administered in this trial for patients of at least 60 years of age.

As described in section 1.2, the dose of clopidogrel in group Phi chosen in this trial (300 mg p.o. initial loading dose followed by 75 mg p.o. qd.) is based on the results of CLARITY, COMMIT and STREAM-1.^{16, 20, 28, 29}

Acetylsalicylic acid is used as routine treatment after acute myocardial infarction and has been shown to be beneficial when combined with tenecteplase in several trials.^{24, 26} Recent guidelines recommend 150 – 325 mg p.o. given immediately, followed by 75 – 100 mg once daily with lifelong treatment unless it is contraindicated.

As for the sequence of treatments, the required dose of tenecteplase administered as a single intravenous bolus over 5-10 seconds should be the first drug injected. Next, the s.c. dose of enoxaparin and then the oral drugs, i.e. clopidogrel and acetylsalicylic acid, should be given.

Pharmacological treatment will be followed by timely coronary angiography after 6 hours but within 24 hours of the start of fibrinolytic therapy and, if required, PCI or, in case of insufficient ST resolution at 90 min (or earlier if clinically indicated), rescue PCI. The time window of 6-24 hours between the start of fibrinolysis and catheterisation avoids interventions when there is still the pro-thrombotic effect of the lytic agent on the one hand and, on the other hand, minimizes the risk of spontaneous reocclusion after successful fibrinolysis. The decision on rescue PCI will, however, be taken 90 min (or earlier if clinically indicated) after injection of tenecteplase according to the ST resolution.³⁵ Rescue PCI will be centrally adjudicated in the core ECG laboratory.

In the PPCI arm, patients will receive antithrombotic treatments as soon as possible according to local standards and international guidelines.

Please also refer to section 1.2 for details.

4.1.4 Selection and timing of doses for each patient

4.1.4.1 Group Phi

Pre-PCI hospital (ambulance/ER community hospital) treatment:

Acetylsalicylic acid

Acetylsalicylic acid is expected to be administered routinely to all patients: a loading dose of 150-325 mg p.o. if not on acetylsalicylic acid already. Alternatively, if the patient is unable to ingest tablets, the initial dose may be given intravenously (80 to 250 mg i.v.). If a patient has already taken acetylsalicylic acid within 12 hours prior to screening the patient will start with acetylsalicylic acid the next day (maintenance dose: 75 to 100 mg).

Tenecteplase

50 or 40 mg of drug reconstituted in sterile water (10 or 8 ml respectively) for injection will be given as single weight-adjusted i.v. bolus over 5 - 10 seconds according to the following scheme:

Weight (kg)	Dose (mg)	Dose (ml)
≥55 to <60	15.0 mg	3.0 ml
≥60 to <70	17.5 mg	3.5 ml
≥70 to <80	20.0 mg	4.0 ml
≥80 to <90	22.5 mg	4.5 ml
≥90	25.0 mg	5.0 ml

The total dose of tenecteplase is injected into an intravenous line of normal saline, as close to the insertion site as possible, using aseptic technique. The total dose is to be injected as a rapid intravenous bolus over 5 - 10 seconds. The intravenous line is to be flushed with normal saline immediately after injection of the tenecteplase bolus to ensure complete drug delivery. Tenecteplase must not be administered in dextrose or Ringer's solution.

The same i.v. line may be used for administration of other medication after flushing the line with a sufficient amount of normal saline prior to the subsequent intravenous injection.

Enoxaparin

< 75 years:

- 30 mg i.v. bolus
- S.c. injections of 1.0 mg/kg every 12 hours until hospital discharge (4 days); the first injection should be given within 15 min of the bolus
- For the first two s.c. injections, a maximum of 100 mg should not be exceeded

≥ 75 years:

- No bolus;
- S.c. injections of 0.75 mg/kg every 12 hours until hospital discharge or for a maximum of

4 days; the first injection should be given immediately

- For the first two s.c. injections, a maximum of 75 mg per injection should not be exceeded

For patients of any age with a creatinine clearance < 30 ml/min, s.c. injections of 0.75 mg/kg will be given in intervals of 24 hours.

Clopidogrel

- 300 mg p.o. initial loading dose (either 4x75 mg or a single 300 mg dose)
- 75 mg p.o. once daily as maintenance dose

In-PCI hospital treatment:

Patients randomised in the ER of a community hospital will be transferred immediately to the PCI hospital after receiving study medication. This is needed to ensure timely rescue coronary intervention if required.⁴⁶ Only community hospitals without a catheterization lab and who have an established transfer protocol with a PCI hospital can participate in the study.

The patient should be admitted to either the emergency department, coronary care unit or catheterisation laboratory (as per local practice).

Assessment of reperfusion (by ECG) and evaluation of clinical symptoms will be done 90 min after injection of tenecteplase or earlier if clinically indicated.

ENOXAPARIN

Continuation of enoxaparin started at randomisation:

<75 years: 1.0 mg/kg SC (max 100 mg) every 12 h (i.v. bolus already given at randomisation)

≥75 years: 0.75mg/kg SC (max 75 mg) every 12 h

Prior to **catheterisation** enoxaparin should be given according to the following scheme (please also refer to chapter 4.2.2 for restrictions).

If cath before 2nd s.c. enoxaparin dose: 0.3 mg/kg iv enoxaparin

If cath after 2 or more s.c. enoxaparin doses and ≤ 8 hr after last dose: no additional enoxaparin

If cath after 2 or more s.c. enoxaparin doses and > 8 hr after last dose: 0.3 mg/kg iv enoxaparin

After sheath removal: further use of s.c.enoxaparin is at the discretion of investigator (e.g. in patients where anti-thrombin treatment is indicated, as in atrial fibrillation etc.)

- Clarifications:

- If catheterisation is performed \leq 8 hours after the second or any later s.c. enoxaparin dose, no additional i.v. enoxaparin should be given (see box above).
- If catheterisation is performed $>$ 8 hours from the second or any later s.c. enoxaparin dose, additional 0.3 mg/kg of i.v. enoxaparin should be administered.

If a closure device is used, the sheath should be removed at the end of the PCI; however, if no closure device is used, the sheath should be removed at least 6 h after the last intravenous or subcutaneous dose of enoxaparin.

After sheath removal further use of s.c. enoxaparin is at the discretion of the investigator (e.g. in patients where antithrombin treatment is indicated, as in atrial fibrillation etc.). If longterm oral anticoagulation is needed (eg because of atrial fibrillation) aspirin may be stopped (at the discretion of local investigator).

Important Note: For patients who received enoxaparin according to the protocol a change to a different type of heparin (e.g., unfractionated heparin) before or during catheterisation should be avoided (cf. 4.2.2).

CLOPIDOGREL

The maintenance dose of clopidogrel (75 mg p.o. per day) should be continued for 1 year.

CATHETERISATION: for details please refer to section 6.2.2.1.

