4.2.2 Restrictions

Enoxaparin and heparin

Patients who received enoxaparin should not be administered a different type of heparin prior to catheterisation (and vice versa) as this may result in excessive anticoagulation well above therapeutic levels.^{47,48} If heparin was initially used for PPCI patients, subsequent treatment should not be switched to enoxaparin prior to catheterisation.

Prior to catheterisation a dose of 0.3 mg/kg i.v. enoxaparin should be given to patients in Group PhI, unless the last subcutaneous dose of enoxaparin was given within the previous 8 hrs.

GP IIb/IIIa antagonists

GP IIb/IIIa antagonists should not be used in Group PhI except if required for bail-out situations in the catheter laboratory. The use of GP IIb/IIIa antagonists in PPCI arm is at the investigator's discretion in accordance with STEMI/PCI guidelines and local standards.

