6.2.2.1 Group Phi

Assessment of reperfusion

At the receiving PCI hospital patients should be admitted to either the emergency department, coronary care unit or catheterisation laboratory (as per local practice) to assess reperfusion.

The patient's need for rescue coronary intervention will be assessed by both ECG and evaluation of clinical symptoms 90 min (or earlier if clinically indicated) after injection of tenecteplase. These patients may undergo coronary intervention immediately, if indicated, in accordance with the protocol criteria described below.

An additional ECG should be taken before starting the procedure. If there are clinical or electrocardiographic signs of reperfusion that have occurred after the previous ECG, the planned coronary intervention may be postponed.

Cardiac Catheterisation

- If ST-segment resolution is $\geq 50\%$ in the qualifying lead (that had the maximum initial ST-segment elevation in the baseline ECG), diagnostic coronary angiography (followed by

elective PCI +/- stenting, if indicated) should be performed no sooner than 6 hours, but within 24 hours after administration of tenecteplase. This will be considered as planned catheterisation according to protocol

- If ST-segment resolution is < 50 % relative to the ST-segment elevation in the qualifying lead at baseline, irrespective of the presence or absence of clinical symptoms, rescue coronary intervention should be performed promptly.
- If any of the following indications require coronary intervention (irrespective of previous ST-segment resolution), urgent coronary intervention is indicated at any time:
 - haemodynamic instability (presence of any of the following requiring inotropic support: sustained hypotension, cardiogenic shock, or congestive heart failure)
 - refractory ventricular arrhythmias requiring cardioversion or pharmacological treatment
 - worsening ischaemia
 - progressive or sustained ST-segment elevation which, in the judgement of the investigator, requires immediate coronary intervention

All rescue and urgent coronary interventions will be adjudicated by an independent clinical expert as previously described.¹⁹ Feedback to participating sites regarding adherence to protocol defined indications for rescue will be provided as appropriate.

Further ECG measurements

Further ECG measurements are listed in Table 4.

Table 4: Overview of ECG measurements in Group PhI

Timing of ECG	Location	Reason for ECG

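### Two protocol sections give opposite pre-catheterisation enoxaparin instructions in the first 8 hours after the first s.c. dose; the enoxaparin rationale for ages 60-74 also differs from the schedule

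*Protocol*

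**What the plan says.** **Enoxaparin before catheterisation, Group PhI.** The box in Protocol 4.1.4.1 separates patients by the number of s.c. doses received. Its first line is "If cath before 2nd s.c. enoxaparin dose: 0.3 mg/kg iv enoxaparin". Its 8-hour exemption starts only after two or more s.c. doses, and the clarifications below keep to that: when catheterisation falls within 8 "hours after the second or any later s.c. enoxaparin dose, no additional i.v. enoxaparin should be given".

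Protocol 4.2.2 (Restrictions) states one rule for all Group PhI patients: 0.3 mg/kg i.v. before catheterisation, "unless the last subcutaneous dose of enoxaparin was given within the previous 8 hrs". It sets no minimum number of s.c. doses.

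The sentence that introduces the box says "please also refer to chapter 4.2.2 for restrictions". The later note in 4.1.4.1 cites 4.2.2 again, for avoiding a switch to another heparin. Neither says which section prevails.

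**Timing of catheterisation.** Protocol 4.1.3: "The decision on rescue PCI will, however, be taken 90 min (or earlier if clinically indicated) after injection of tenecteplase". Protocol 6.2.2.1: with insufficient ST resolution, "rescue coronary intervention should be performed promptly"; otherwise planned angiography takes place "no sooner than 6 hours, but within 24 hours after administration of tenecteplase".

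**Initial enoxaparin.** Protocol 4.1.3 says that for patients aged 60 or more, which is everyone in the trial, the i.v. bolus is left out and 0.75 mg/kg replaces 1 mg/kg. Its sequence of drugs has no i.v. enoxaparin step. Protocol 1.4 also says the bolus is left out, without an age limit. The schedule in 4.1.4.1 gives patients under 75 a 30 mg i.v. bolus and 1.0 mg/kg s.c. every 12 hours, and the in-hospital text repeats this. For patients aged 75 or more the sections agree.

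**The concern.** Protocol 1.4 names bleeding as the main risk of fibrinolysis. Staff who take a lytic-treated patient to early catheterisation find one section that calls for an i.v. anticoagulant dose and another that exempts the patient from it. The choice also affects later care: without a closure device, 4.1.4.1 times sheath removal from the last i.v. or s.c. enoxaparin dose.

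The second discrepancy is of a different kind. Protocol 6.2.1 sends staff to section 4.1.4 for treatment details, so the schedule there is the operative text. The benefit/risk and dose-selection sections, however, describe a lower enoxaparin exposure than patients aged 60-74 are scheduled to receive.

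There is a smaller consequence for the analysis. SAP Table 1 counts failure to receive the correct enoxaparin dose as a major protocol deviation, and SAP section 4 removes patients with major violations from the per-protocol set. A correct dose then needs a single written definition.

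**Working it through.** The plan gives no figure to reproduce, so the check sets the rules side by side and then sizes the affected period.

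**Step 1. The two pre-catheterisation rules.**

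| Situation at catheterisation | Box, 4.1.4.1 | Section 4.2.2 |
|---|---|---|
| One s.c. dose, given up to 8 h ago | 0.3 mg/kg i.v. | none required |
| One s.c. dose, given more than 8 h ago | 0.3 mg/kg i.v. | 0.3 mg/kg i.v. |
| Two or more, last up to 8 h ago | none | none required |
| Two or more, last more than 8 h ago | 0.3 mg/kg i.v. | 0.3 mg/kg i.v. |

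Only the first row conflicts. The rules were compared in 0.1-hour steps from 0.5 to 24 hours after the first s.c. dose. They differed at every step up to and including 8.0 hours and at none after it. The result was the same with 12-hour dosing and with the 24-hour interval used when creatinine clearance is below 30 ml/min.

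**Step 2. Does catheterisation fall in that period?** The first s.c. dose is due within 15 minutes of the bolus (under 75) or immediately (75 and over), so it is taken here as given at about the time of tenecteplase.

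- Rescue is decided at 90 minutes or earlier and done promptly, which is inside the first 8 hours.
- The planned window is 6-24 hours. The overlap is 8 − 6 = 2 of 24 − 6 = 18 hours. The number of planned procedures in those 2 hours is not stated.

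**Step 3. Number of patients.** Inputs: 400 PhI patients (Protocol 3.3) and an anticipated rescue rate of about 25-30% (Protocol 5.3.3).

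- All rescues within 8 hours: 0.25 × 400 = 100 to 0.30 × 400 = 120.
- 80% within 8 hours (assumed): 0.80 × 100 = 80 to 0.80 × 120 = 96.
- Range over 80-100% within 8 hours: 80-120.
- At the urgent-intervention rate of at least one third that Protocol 1.1 reports for STREAM-1: 400/3, about 133, if all are within 8 hours.

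**Step 4. Amount of drug.** 0.3 × weight from the 55 kg entry limit to 100 kg: 16.5 mg at 55 kg, 24 mg at 80 kg, 30 mg at 100 kg. As a share of the scheduled first s.c. dose: 0.3/0.75 = 40% at 75 and over, 0.3/1.0 = 30% below 75.

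**Step 5. Rationale against schedule, ages 60-74.**

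| | 4.1.3 | 1.4 | 4.1.4.1, under 75 |
|---|---|---|---|
| Initial i.v. bolus | none | none | 30 mg |
| s.c. dose | 0.75 mg/kg | no figure | 1.0 mg/kg |

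The s.c. ratio is 1.0/0.75 = 1.33. Adding i.v. and s.c. milligrams, which assumes that the routes are equivalent, the first administration compares as (30 + 1.0 × kg)/(0.75 × kg): 85/41.25 = 2.06 at 55 kg, 110/60 = 1.83 at 80 kg, 130/75 = 1.73 at 100 kg. The documents give no number of patients aged 60-74, and none is assumed. Patients with creatinine clearance below 30 ml/min follow a separate s.c. rule.

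**The case against.** **The box is specific and 4.2.2 is a summary.** Four lines of 4.1.4.1 (two in the box, two clarifications) tie the 8-hour limit to the second or a later dose. Section 4.2.2 is a single sentence, worded as an exception and not as a ban, in a section mainly about other drugs. The pointer in 6.2.1 to section 4.1.4 makes the schedule operative for initial dosing, and it would equally favour the box. This reading is available, but the text does not compel it. The introduction to the box itself sends the reader to 4.2.2 for restrictions, and no section states precedence. If 4.2.2 governs, the first line of the box is wrong for 8 hours; if the box governs, 4.2.2 is too broad. Either way one of them has to change.

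**The consequence for the analysis is small.** This stands. SAP section 4 bases the primary analyses on the FAS and uses the per-protocol set for sensitivity only. Exclusions are already decided case by case, blinded to outcome. It is not stated whether the pre-catheterisation dose is judged under the enoxaparin row of SAP Table 1, and Table 5.1 tabulates milligrams only for the first two s.c. injections.

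**Dosing may be over.** The SAP is dated 17 November 2022 and the planned trial period ended in June 2022. If nobody is still being dosed, what remains is the protocol record and the classification of deviations.

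**The sizes are soft.** The 100-120 is an expected count, not a ceiling. The 80% has no source in the documents. The summed-route ratio rests on an equivalence that they do not support; the text itself supports only 30 mg or no bolus and the 1.33-fold s.c. dose. Protocol 1.4 bears on the bolus alone.

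**Conclusion.** The concern holds. For PhI patients catheterised within 8 hours of the first s.c. enoxaparin dose, 4.1.4.1 gives 0.3 mg/kg i.v. and 4.2.2 exempts them. The period is one the protocol plans for. The difference is 16.5-30 mg or none at 55-100 kg, for an expected 80-120 of 400 PhI patients through rescue alone, on the protocol's 25-30% rate and an assumed 80-100% of rescues within 8 hours. Planned procedures at 6-8 hours would add to that.

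The need to correct the text rests on this first part. The second part also holds but is lesser: 4.1.3 and, for the bolus, 1.4 do not describe what 4.1.4.1 gives patients aged 60-74. That is a rationale out of step with the schedule, not two competing instructions. FAS results do not depend on either part.

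**What to change.** The sponsor's clinical leads should reconcile Protocol 1.4, 4.1.3, 4.1.4.1 (initial schedule, in-hospital continuation and pre-catheterisation box) and 4.2.2 into one consistent enoxaparin text. Which regimen it adopts is for them to decide. If patients are still being dosed, sites should be notified.

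The Analysis Sets Specification Document should name the reconciled text as the reference for the enoxaparin row of SAP Table 1, and say whether the pre-catheterisation dose is judged under that row. It should also state, before database lock and blinded to outcome, how patients treated under either written version are classified.

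The cost is wording changes in those protocol sections and a few sentences in a document that SAP section 4 already requires. Neither the design nor the analyses change.
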